4.2 Hypothesis

We will test the following null hypothesis:

$$H_0 : \pi_{\text{anti-platelet treatment}} \geq \pi_{\text{anti-coagulant treatment}} + \delta \quad (1)$$

where δ is the non-inferiority margin. The alternative hypothesis is:

$$H_1 : \pi_{\text{anti-platelet treatment}} < \pi_{\text{anti-coagulant treatment}} + \delta \quad (2)$$

where π is the probability of a CIHD under the indicated treatment.

The non-inferiority margin is set to $\delta = 0.12$ (12 % absolute risk difference).

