4.3 Model and method of analysis

The difference in CIHD rate $\pi_{\text{anti-coagulant treatment}} - \pi_{\text{anti-platelet treatment}}$ will be compared with the non-inferiority margin using a two-sided 95 % confidence interval. We will use Wilson's method to calculate CI (continuity-corrected modification of the Wilson's score method [Newcombe, 1998](#)). The primary analysis will be performed on the PP. Section 5.2 describes the handling of missing values.

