4.5 Supportive analyses and sensitivity analyses

The following supportive and sensitivity analyses will be conducted to support the main analysis described above (Section 4.3). The rationale for each sensitivity analysis is indicated in bold. All sensitivity analyses except for the sensitivity analysis nr 2 will be performed on the PP. Missing values will be handled as described in section 5.2 if not defined otherwise.

1. **Missing values:** In case of missing values for the primary endpoint, the main analysis will be repeated performing the following imputations

³In the protocol, this was planned as sensitivity analysis. However, given the rather young patient population, we do not expect preexisting micro- or macrobleeds. Therefore the probability of falsely labeling an existing microbleed as new due to missing baseline T2* - or SWI MRI was considered to be small and the aim to preserve the randomization was of overriding importance. Therefore the two analyses were switched.

- (a) Missing values in the primary endpoint will be imputed as CIHD events (assuming the worst for patients without follow-up).
 - (b) Missing values in the primary endpoint will be imputed as no CIHD events (assuming the best for patients without follow-up).
2. **Choice of analysis population (PP vs. FAS):** The analysis will be repeated on the FAS and compared to the main analysis. According to the intention-to-treat principle, each patient will be analyzed according to the treatment she/he was randomly allocated to. In case of missing values for the primary endpoint, the following imputations will be performed:
 - (a) Missing values in the primary endpoint will be imputed as CIHD events (assuming the worst for patients without follow-up).
 - (b) Missing values in the primary endpoint will be imputed as no CIHD events (assuming the best for patients without follow-up).
 - (c) Patients with missing values in the primary endpoint will be excluded from the analysis. Inverse probability of censoring weights will be used as described for the main analysis in section 5.2.
3. **Incomplete information about micro- or macrobleeds at baseline:** The main analysis will be repeated excluding patients without baseline information with regards to micro- or macrobleeds.

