4. **Effect of failure to preserve the randomization due to major protocol deviations:**⁴ We will use stabilized inverse probability weights to assess the impact of patients excluded from the PP analysis set according to (Robins et al., 2000) and (Hernan & Robins, 2006; Austin & Stuart, 2015). The weights will be estimated on the FAS. Thereby we will use the following variables: age, sex, occlusion of dissected artery and National Institutes of Health Stroke Scale (NIHSS). If the patient did not have a stroke, 0 will be imputed for the NIHSS. Thereafter the main analysis will be repeated including the weights. By doing so, patients without deviation who are similar to the patients with deviation will be inflated (compared to and patients without similarities).
5. **Assessing a modelling approach:** we compare the probability of CIHD between trial arms using a logistic regression model. The incidence of CHID will be the dependent variable. Treatment will be used as independent factor. In addition, the model will include the presence of cerebral ischemic events clinically and/or neuroradiologically (i.e., clinically defined ischemic stroke, or DWI-lesions at baseline, or both) and occlusion of the dissected artery as covariates to adjust for baseline differences among patients.
6. **Effect of minor protocol deviation:**⁵ The main analysis will be repeated excluding patients who were randomized or initiated treatment more than 72h after initial MRI scan, which was considered to be a minor protocol deviation.

⁴This sensitivity analysis was not planned in the protocol. However we think it helps to further assess the potential bias introduced when randomized patients are excluded from the analysis set due to major protocol deviations.

⁵This sensitivity analysis is a consequence of the adaption in section 2 ("major" vs. "minor" protocol deviations).

7. **Effect of imaging endpoint (as compared to clinical endpoints):**⁶ The main analysis will be repeated including only the clinical endpoints ICH, stroke, extracranial hemorrhage and death as components of the primary endpoint.

All patients with a primary or secondary outcome event will be listed by the PI. For the primary outcome events, the PI will provide information on type, timepoint of the outcome event and relation to the allocated treatment (antiplatelets vs anticoagulants). Laboratory values quantifying coagulation at the time of the event will be provided if available.

5 Secondary objective

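### Sensitivity analysis 7 carries the 12-point margin set for the full CIHD composite over to clinical events alone, where meeting it is weak evidence of non-inferiority

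*SAP*

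**What the plan says.** SAP section 4.2 fixes a single margin, "12 % absolute risk difference", and ties it to one parameter: "where π is the probability of a CIHD under the indicated treatment". CIHD, defined in section 4.1, includes two imaging-only components: new acute DWI lesions (item 1b) and new asymptomatic micro- or macrobleeds (item 2c).

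Section 4.3 defines the main analysis. The difference in CIHD rates "will be compared with the non-inferiority margin using a two-sided 95 % confidence interval", the interval is the "continuity-corrected modification of the Wilson's score method", and "The primary analysis will be performed on the PP".

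Section 4.5, analysis 7, then says: "The main analysis will be repeated including only the clinical endpoints ICH, stroke, extracranial hemorrhage and death as components of the primary endpoint". It gives no separate margin, no relative measure and no rule for reading the result. Footnote 6 gives two reasons for the analysis: the meaning of DWI lesions is debated, and the result can be set beside studies that used clinical endpoints only. The introduction to section 4.5 says that supportive and "sensitivity analyses will be conducted to support the main analysis described above".

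**The concern.** Among the analyses in section 4.5 that repeat the main analysis, number 7 is the only one that changes the endpoint. Numbers 1 to 4 and 6 change the patients, the imputation or the weights but keep CIHD, so the margin keeps its meaning. Number 5 is a logistic model without a margin. Number 7 removes both imaging components and leaves the margin as it is.

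Removing components from a composite can only lower the event rate or leave it unchanged. A fixed absolute margin then allows at least as large a relative excess as before, and possibly a much larger one. At stake is the reading of this analysis. It is the one meant to answer doubts about the imaging endpoint, so an upper limit below 12 points could be cited as clinical support for non-inferiority when it shows little.

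**Working it through.** **Inputs from the SAP.** Margin 0.12 (section 4.2). Two-sided 95% interval, so z = 1.96 (section 4.3). Difference interval built from continuity-corrected Wilson limits (section 4.3). The SAP states no sample size, power or event rate, so it has no figure to reproduce.

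**Assumptions.** Equal arms, 50 to 150 evaluable patients per arm, no missing outcomes, no censoring weights (section 5.2), and control-arm clinical risks of 1% to 5%.

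**Risk at the edge of the margin (control risk + 12 points).** 1% → 13% (13-fold); 2% → 14% (7-fold); 3% → 15% (5-fold); 5% → 17% (3.4-fold).

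**Interval.** For x events in n, with p = x/n and q = 1 − p:

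- L = [2np + z² − 1 − z√(z² − 2 − 1/n + 4p(nq + 1))] / [2(n + z²)], with L = 0 if x = 0
- U = [2np + z² + 1 + z√(z² + 2 − 1/n + 4p(nq − 1))] / [2(n + z²)]

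With arm 1 antiplatelet, arm 2 anticoagulant and d = p1 − p2:

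- lower = d − √((p1 − L1)² + (U2 − p2)²)
- upper = d + √((U1 − p1)² + (p2 − L2)²)

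The criterion is upper < 0.12. Section 4.3 writes the difference the other way round; the criterion is the same with the sign reversed.

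**Observed counts at an assumed 90 per arm.**

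- 4 vs 0: p1 = 4.44%, L1 = 1.43%, U1 = 11.62%; p2 = L2 = 0, U2 = 5.10%. Upper = 4.44 + (11.62 − 4.44) = 11.6. Lower = 4.44 − √(3.01² + 5.10²) = −1.5. Meets the margin.
- 5 vs 2: upper limit 11.1. Meets it.
- 5 vs 1: d = 4.44, U1 = 13.08%, L2 = 0.06%. Upper = 4.44 + √(7.52² + 1.05²) = 12.04. Does not meet it.
- 5 vs 0 (upper limit 13.1) and 6 vs 2 (12.5) do not meet it.

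**Probability of meeting the margin under true risks.** For each control count c, let m(c) be the largest antiplatelet count with upper < 0.12. The probability is the sum over c of P(C = c) × P(X ≤ m(c)), with both counts binomial.

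| True risks, antiplatelet vs anticoagulant | n = 50 | n = 75 | n = 90 | n = 100 | n = 150 |
|---|---|---|---|---|---|
| 4% vs 1% | 0.262 | 0.570 | 0.746 | 0.821 | 0.962 |
| 6% vs 2% | 0.202 | 0.398 | 0.519 | 0.592 | 0.822 |
| 8% vs 2% | 0.100 | 0.195 | 0.267 | 0.310 | 0.499 |
| 9% vs 3% | 0.105 | 0.187 | 0.261 | 0.286 | 0.457 |
| 15% vs 5% | 0.027 | 0.039 | 0.046 | 0.049 | 0.063 |

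The result depends strongly on both unknowns. The criterion is lenient at low control risks with about 75 or more per arm. It is demanding with small arms, where the interval is wide, and at higher control risks.

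**The case against.** The strongest reply is that the SAP attaches no non-inferiority decision to analysis 7. Its hypotheses concern CIHD only, section 4.5 calls these analyses supportive, and both aims in footnote 6 can be met by estimation. An excess would also be visible: section 4.4 provides the point estimate and interval, section 5.1 tabulates strokes, major extracranial bleeds, symptomatic intracranial bleeds and deaths on both analysis sets, and section 4.5 has all outcome events listed. All of that stands, and it limits the severity. It does not remove the point, because repeating the main analysis includes its comparison with the margin and nothing tells the reader to set that comparison aside. The exploratory caveat in section 5.1 covers secondary endpoints, not section 4.5.

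A reader might infer more: that clinical events are rare here, that 12 points exceeds the whole expected risk in either arm, or that the analysis would pass despite any several-fold excess and so tells us almost nothing. The SAP does not support these readings. It gives no event rate and no sample size; only the direction of the change in rate follows from it. At an assumed 90 per arm, 5 vs 0, 5 vs 1 and 6 vs 2 events all fail the criterion, so it does discriminate.

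**Conclusion.** The carry-over of the margin stands on the text alone: a margin set for the imaging-inclusive composite is applied, without justification, to clinical events only. How lenient this is rests on assumed rates and arm sizes. For 4% vs 1% or 6% vs 2% with 75 to 150 per arm, the margin is met in roughly 40% to 96% of trials; a steeper excess at 2% control risk (8% vs 2%) passes less often, in about 20% to 50%. With 50 per arm, or with a control risk of 3% to 5% and up to about 100 per arm, the interval mostly blocks a three-fold excess. Meeting 12 points in this analysis is therefore weak evidence of clinical non-inferiority, though not empty evidence. The primary analysis, its margin and its conclusion are untouched. Severity is minor.

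**What to change.** In SAP section 4.5, analysis 7, state that the clinical-only composite is reported as event counts by arm with the risk difference and its 95% CI, that it is not compared with the 12-point margin, and that no non-inferiority conclusion is drawn from it.

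This is a change of wording only and needs no new data; the estimate and interval are already planned. The sponsor gives up a non-inferiority statement for the clinical-only endpoint. Both purposes in footnote 6 are still served.

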5.1 Secondary endpoints

1. new ischemic strokes (including retinal infarction)
2. new acute lesions on diffusion-weighted MRI
3. any major extracranial hemorrhage
4. any symptomatic intracranial hemorrhage
5. any asymptomatic micro- or macro-bleeds
6. any death
7. any increase in volume of the vessel wall hematoma on follow-up cervical MRI as compared to the baseline MR-scan.
8. modified Rankin scale at 3 and 6 months
9. independence in activity of daily living (i.e. modified Rankin scale 0-2) at 3 months and at 6 months
10. excellent functional outcome (i.e. modified Rankin scale 0 or 1) at 3 and 6 months
11. any TIA (classical definition)
12. recurrent cervical artery dissection

All secondary endpoints will be presented descriptively. The particular events leading to the primary endpoint (1 – 6) will be summarized as frequencies and percentages. If patients died while under observation (endpoint 6), we will provide the number of patients with cerebrovascular death. Patients with more than one event will be listed. Time between treatment initiation and event will be presented. The summaries will be done on the PP as well as on the FAS.

⁶This sensitivity analysis is planned since the significance of DWI lesions is still debatable. It also allows to compare the results with studies assessing only clinical endpoints.

The effect of treatment (anti-platelet vs. anti-coagulation) on mRS at three months (endpoint 8) will be assessed in a proportional odds model (also called ordinal logistic regression or shift-model). "Independence in activity" and "excellent functional outcome" at three months (endpoints 9 and 10) will be modelled in logistic regression models. Presence of cerebral ischemic events clinically and/or neuradiologically (i.e., clinically defined ischemic stroke, or DWI-lesions at baseline, or both), occlusion of the dissection arteries and mRS before dissection will be included as covariates to adjust for baseline differences among patients. The models will be fit on the PP.

The analyses of other endpoints, described as tertiary endpoints in the study protocol, will be described elsewhere. This also includes the interaction tests of antiplatelet versus anti-coagulant treatment and MMP9/TIMP2 ratio or other biomarker signatures.

All analyses of the secondary endpoints are explorative. Results have to be interpreted as hypothesis generating and not as confirmatory. P-values should be interpreted as continuous measure of evidence against the corresponding null-hypothesis (i.e. no association with predictor) and not as confirmatory ("significant" vs. "non-significant"). No correction for multiple testing will be performed.

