Biomarkers and antithrombotic treatment in cervical artery dissection
The TREAT-CAD trial

ClinicalTrials.gov Identifier: NCT 02046460

Statistical analysis plan – dated Dec. 18th 2019

[name]. [name]
Universitätsspital Basel
Neurologie
[name]
[name]

Basel, December 18, 2019

Methods & Statistics

Study Title	Biomarkers and antithrombotic treatment in cervical artery dissection
Internal DKF ID	[name]
Document Status	Confirmed Final Report

This statistical report and analysis plan will be finalized before database closure and will be under version control at the Clinical Trial Unit, University Hospital Basel.

1 Background

Antithrombotic treatment in cervical artery dissection (CAD) is still a matter of debate. Most physicians prescribe anticoagulants for stroke prevention in CAD-patients although this approach is not evidence-based.

This randomized controlled, open labeled multicenter non-inferiority trial with blinded assessment of outcome events compares anticoagulant treatment to antiplatelet treatment.

2 Analysis data sets

The **full analysis set (FAS)** consists of all patients that were randomized. According to the intention-to-treat principle, each patient will be analyzed according to the treatment she/he was randomly allocated to. Patients who withdrew their consent during the course of the study will be analyzed in the FAS including only their baseline data.

The **per protocol set (PP)** consists of patients in the FAS set without any of the following major protocol deviation:

- no dissection: diagnostic criteria for CAD not met in central MR reading
- violation of an inclusion criterion or having an exclusion criterion (for pregnancy, only a positive pregnancy test will be considered as a major protocol deviation)¹
- switching between treatment groups (cross-over) or discontinuation of the allocated treatment before follow-up visit 2 for any reason other than as a reaction to a primary outcome-event or an SAE
- MRI at follow-up visit 1 earlier or later than 14 +/- 10 days
- follow-up visit 2 prior to 60 days after randomization ²

The following deviations will be considered as minor protocol deviations:

- result of pregnancy test too late but negative (ie. confirmed absence of pregnancy after inclusion and randomization)
- randomization or start of treatment allocated not within 72h after initial MRI scan

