5.2 Missing values

Primary endpoint In patients with missing information on micro- or macrobleeds at baseline, any lesion detected on follow-up T2*- or SWI MRI will be considered as new lesion (section 4.1 and sensitivity analysis 3). For missing values in the primary endpoint (e.g. due to missing follow-up), inverse probability of censoring weights will be estimated. Thereby stabilized inverse probability of weights for missingness of the primary endpoint will be estimated for each treatment arm according to (Robins et al., 2000) and (Hernan & Robins, 2006; Austin & Stuart, 2015). The weights will be estimated on the PP except for the sensitivity analysis 2, where the FAS will be used. The following variables will be used to estimate the weights: age, sex, occlusion of dissected artery, and National Institutes of Health Stroke Scale (NIHSS). If the patient did not have a stroke, 0 will be imputed for the NIHSS. Missing values will be further investigated in sensitivity analyses (see sensitivity analysis 1).

Covariates Missing values in covariates used to estimate the inverse probability of censoring weights will be imputed. If the number of missing values does not exceed 5% in each variable of interest the median (continuous variables) or the mode (= most frequent category, categorical variables) will be used. If there is one covariate with more than 5% missing values, 5 multiple imputations will be done as described in van Buuren & Groothuis-Oudshoorn (2011). To this end we will generate 5 imputed data sets. In a second step we will estimate the weights for each imputed data set. Thereafter, we will stabilize and average the weights over the 5 imputations. In case of severe variability of the stabilized weights between imputations, we will increase number of imputations. Thereby the weights will be considered to have "severe variability between imputations" if for any patient the inter-weight variability divided by the number of imputations (the amount the variance would be increased in order to correct for the uncertainty of the imputations when using Rubin's rule, Barnard & Rubin (1999)) is larger than 0.01.

Secondary endpoints: The number of missing values will be presented. No imputations will be performed. Secondary analyses will be complete case analyses.

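### The three-month functional-outcome models estimate a treatment difference on the per-protocol set only; they should be led by a fit on the full analysis set by randomized arm

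*SAP*

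**What the plan says.** Section 5.1 of the SAP lists twelve secondary endpoints. Three of them receive a modelled treatment comparison:

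- Endpoint 8: "The effect of treatment (anti-platelet vs. anti-coagulation) on mRS at three months (endpoint 8) will be assessed in a proportional odds model".
- Endpoints 9 and 10 (mRS 0-2 and mRS 0-1): "at three months (endpoints 9 and 10) will be modelled in logistic regression models".

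The covariates are cerebral ischemia at baseline, occlusion of the dissected artery and mRS before the dissection. On the analysis set the section says: "The models will be fit on the PP".

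The same section says of the descriptive part: "All secondary endpoints will be presented descriptively", and "The summaries will be done on the PP as well as on the FAS". Its last paragraph declares all secondary analyses exploratory and gives their null hypothesis as no association. Section 5.2 adds: "Secondary analyses will be complete case analyses".

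Section 2 defines the two sets. The FAS "consists of all patients that were randomized", analysed as allocated. The PP removes patients with major deviations and analyses the others by the treatment received up to visit 2. Among the deviations are a change to the other arm's treatment and, within the same item and under the same exception, "discontinuation of the allocated treatment before follow-up visit 2 for any reason other than as a reaction to a primary outcome-event or an SAE".

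**The concern.** A PP analysis is commonly defended in a non-inferiority trial because poor adherence in an intention-to-treat analysis can pull the arms together and so favour a claim of non-inferiority. That defence belongs to the primary endpoint, which is tested against a margin of 12 percentage points. The functional models have no margin. For a question about a difference, the randomized comparison is the natural main analysis, and the SAP gives no reason for leaving it.

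At stake is the only modelled evidence on disability. If the patients removed from the PP differ in function from those kept, and differ in one arm more than in the other, the odds ratios can show a difference that the randomized groups do not have, or miss one that they do. Adjustment for baseline covariates cannot be relied on to correct selection on what happened after randomization.

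**Working it through.** The SAP has no figure to reproduce here. The check sets its sections side by side, followed by one labelled illustration.

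**1. Which PP exclusions arise after randomization (section 2)?**

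| Major deviation | When it arises | Bearing on three-month mRS |
|---|---|---|
| No dissection on central reading | Baseline condition | Defines the population |
| Eligibility violation | Baseline condition | Defines the population |
| Cross-over or stopping before visit 2, unless in reaction to a primary event or SAE | After randomization | May be related to function |
| Visit 1 MRI outside 14 +/- 10 days | After randomization | None evident; it concerns imaging |
| Visit 2 before day 60 | After randomization | Some, if the three-month mRS is taken at visit 2 |

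Three of the five arise after randomization. The third row also makes membership depend on the course of disease: a patient who stops after an event stays in, and a patient who stops for another reason is removed.

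**2. Do other parts of the SAP cover these models?**

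- Sensitivity analysis 2 (section 4.5) repeats the primary analysis on the FAS. It does not extend to endpoints 8-10.
- Sensitivity analysis 4 reweights for patients excluded from the PP, again for the primary analysis only. Its footnote gives possible bias from such exclusions as the reason for adding it.
- Section 5.2 provides censoring weights for the primary endpoint. Secondary endpoints get complete cases.

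No FAS fit and no weighting is planned for the functional models.

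**3. What drives the size?**

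For a binary outcome such as mRS 0-1, let arm *k* have an excluded fraction *e_k*, a success rate *r_k* in patients kept and *x_k* in patients excluded. Ignoring missing outcomes and differences between allocated and received treatment:

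- PP difference = r_A - r_B
- FAS difference = [(1 - e_A) r_A + e_A x_A] - [(1 - e_B) r_B + e_B x_B]
- FAS minus PP = e_A (x_A - r_A) - e_B (x_B - r_B)

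None of these inputs is in the SAP. Assumed example: 100 patients per arm, e = 10% in both, r = 70% in both, x_A = 40%, x_B = 70%.

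- FAS, arm A: 0.9 x 70 + 0.1 x 40 = 67%; arm B: 70%; difference -3 points.
- PP: 70% against 70%; difference 0.

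Range of the shift, with equal exclusion and a deficit in the excluded patients of one arm only (all values assumed):

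| Excluded per arm | Deficit 0 | Deficit 15 points | Deficit 30 points |
|---|---|---|---|
| 5% | 0 | 0.75 | 1.5 |
| 10% | 0 | 1.5 | 3.0 |
| 20% | 0 | 3.0 | 6.0 |

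If the excluded fraction and the deficit are the same in both arms, the two terms cancel and the shift is 0.

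For scale, the standard error of the FAS difference in the example is sqrt(0.67 x 0.33/100 + 0.70 x 0.30/100) = 0.066, a 95% half-width of 1.96 x 6.6 = about 13 points.

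**The case against.** The choice of the PP is stated plainly, matches the primary analysis set and contradicts nothing in the SAP. The analyses are declared exploratory, with a warning against reading P-values as significant or not. These points stand, and they limit the importance of the matter. They do not remove selection from the estimate.

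The descriptive FAS summaries may already show part of the picture. If they cover endpoints 8-10, as the opening sentence of that paragraph suggests, the unadjusted mRS results in the FAS will be reported, and only the adjusted treatment effect is missing. The sentence on the summaries could also be read as covering the component events 1-6 only. The PP-only modelling stands under either reading.

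Patients who stop or switch in reaction to a primary event or an SAE remain in the PP. They are plausibly among the most disabled, so a reader who infers that the PP removes everyone who stopped, or everyone who fared badly, goes too far. The same holds for treating all PP exclusions as events after randomization: two of the five are baseline conditions.

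A reader might also infer that the FAS fit would be unbiased. The SAP does not support that. Under section 2, patients who withdrew consent contribute baseline data only, and section 5.2 would keep the FAS fit to complete cases.

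**Conclusion.** The point holds as an analysis-choice weakness of moderate weight. Three models that ask about a treatment difference are tied to a set that loses randomized patients partly for reasons after randomization, with analysis by treatment received. The safeguards that the SAP gives the primary endpoint against this are not extended to them. The conclusion rests on the text of sections 2, 4.5, 5.1 and 5.2 and on no assumed number.

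The size and direction of any bias cannot be derived from the SAP. The 3-point example depends wholly on its assumptions, is small beside the sampling error at the assumed 100 per arm, and does not show that a bias of that size exists. The primary non-inferiority conclusion is not affected.

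**What to change.** In section 5.1, replace the sentence that assigns the models to the PP with text to this effect: the proportional odds model for endpoint 8 and the logistic models for endpoints 9 and 10 are fitted on the FAS, with each patient in the randomized arm, as the main secondary models; the same models are repeated on the PP as supportive analyses. Report by arm how many randomized patients drop out of each fit for missing mRS or covariates, and state that the FAS fit is complete case and has no outcomes for patients who withdrew consent.

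The FAS is already defined and used for the primary endpoint, so the extra work is the same code on an existing data set. The cost is a second set of model results to report and, where the two sets differ, to explain. Naming the FAS fits as the main ones in advance settles which set leads.
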